12.3 Adverse Event Relationship to Investigational Product

Any TEAEs attributable to piflufolastat (^{18}F) **will not be** assigned causality (related/not related to piflufolastat (^{18}F)).

The relationship of an AE to the IP (flotufolastat (^{18}F)) will be assessed using the following guidelines in [Table 5](#).

Table 5: AE Relationship to IP (Flotufolastat (^{18}F))

Relationship to IP	Comment
Definitely	Previously known toxicity of agent; or an event that follows a reasonable temporal sequence from administration of the IP; that follows a known or expected response pattern to the suspected IP; that is confirmed by stopping or reducing the dosage of the IP; and that is not explained by any other reasonable hypothesis.
Probably	An event that follows a reasonable temporal sequence from administration of the IP; that follows a known or expected response pattern to the suspected IP; that is confirmed by stopping or reducing the dosage of the IP; and that is unlikely to be explained by the known characteristics of the patient's clinical state or by other interventions.
Possibly	An event that follows a reasonable temporal sequence from administration of the IP; that follows a known or expected response pattern to that suspected IP; but that could readily have been produced by a number of other factors.
Unrelated	An event that can be determined with certainty to have no relationship to the IP.

Abbreviations: ^{18}F =fluorine-18; AE=adverse event; IP=investigational product.

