8.7 Dosage/Dosage Regimen

Each patient will receive piflufolastat (^{18}F) first (Day 1; Visit 2), followed at least 24 hours later, but within 10 calendar days, by flutufolastat (^{18}F). Both radiopharmaceuticals will be administered as single doses according to their respective approved USPIs.

For the IP (flutufolastat (^{18}F) injection), the recommended amount of radioactivity to be administered is $296 \pm 20\%$ MBq ($8 \pm 20\%$ mCi) administered as an IV bolus injection.

See [PYLARIFY USPI](#) and [POSLUMA USPI](#) for further details.

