12.4.2 Suspected Unexpected Serious Adverse Reactions

Suspected unexpected serious adverse reactions (SUSARs) will be collected and reported for the IP, flutufolastat (^{18}F).

A serious adverse reaction is an adverse reaction, the nature and severity of which is not consistent with the reference safety information set out in the approved USPI for flutufolastat (^{18}F).

The sponsor will be responsible for reporting all SUSARs for flutufolastat (^{18}F) to the relevant authorities, IEC/IRB and other parties, as applicable.

Investigators will be informed of all SUSARs for flutufolastat (^{18}F) for all studies sponsored by BED, whether or not the event occurred in the current study.

As detailed in [Section 12.1](#), suspected adverse reactions for piflufolastat (^{18}F) should be reported to the Marketing Authorization Holder (Progenics Pharmaceuticals, Inc) or the FDA as detailed in the [PYLARIFY USPI](#).

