17.4 Post-trial Care

Both radiopharmaceuticals used in this Phase 4 study are single-use diagnostic agents. No additional care for trial patients is therefore planned once their participation in the study has ended. All patients will receive standard of care treatment in line with their medical condition as determined by their physician.

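### The causality scale in Protocol Table 5 does not fit a product given once: *Probably* cannot be reached, and a well-timed reaction new in nature meets none of the four levels

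*Protocol*

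**What the plan says.** Protocol Section 12.3 states that the relationship of an adverse event to flotufolastat "will be assessed using the following guidelines in" Table 5. The table has four levels.

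- *Definitely* has two limbs. It opens with "Previously known toxicity of agent; or an event that follows a reasonable temporal sequence from administration of the IP". The second limb then adds a known or expected response pattern and an event "that is confirmed by stopping or reducing the dosage of the IP; and that is not explained by any other reasonable hypothesis".
- *Probably* has one set of joint conditions: timing, a known or expected pattern, and an event "that is confirmed by stopping or reducing the dosage of the IP; and that is unlikely to be explained by the known characteristics" (meaning the patient's own condition) or by other interventions.
- *Possibly* drops the stopping or reducing condition. It keeps timing and the known or expected pattern, and adds that other factors could readily account for the event.
- *Unrelated* is "An event that can be determined with certainty to have no relationship to the IP".

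On exposure, Protocol Section 8.7 says: "Both radiopharmaceuticals will be administered as single doses according to their respective approved USPIs". Section 17.4 says: "Both radiopharmaceuticals used in this Phase 4 study are single-use diagnostic agents".

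The causality call is used in several places. Protocol Section 12.4.2 says: "Suspected unexpected serious adverse reactions (SUSARs) will be collected and reported for the IP", flotufolastat. Protocol Section 15.5 and SAP Section 7.2 tabulate TEAEs by relationship to flotufolastat, and the SAP does the same for serious TEAEs. SAP Table 3 also assigns events judged related to flotufolastat as attributable to it. SAP Section 2.4.4 counts missing causality as related.

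**The concern.** Table 5 reads as if written for a drug given repeatedly, where an investigator can withdraw or lower the dose and see whether the event resolves. Here there is one bolus per patient, so that confirmation can never be obtained. The scale also ties every related route to something already known: a known toxicity, or a known or expected pattern.

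The event that matters most for safety surveillance, a plausible reaction of a kind not seen before, then has no box. The investigator must choose a level whose definition is not met or leave the field empty. Two sites could handle the same event in opposite ways: one forces *Unrelated*, the other leaves a blank that the SAP turns into related. The affected outputs are the SUSAR classification, the SAP's related TEAE and serious TEAE tables, and attribution under SAP Table 3.

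**Working it through.** The plan gives no figure to reproduce. The check is logical: list the conditions of each level, then see which can be met after a single dose.

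**Step 1. Conditions in Table 5**

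| Level | Reasonable timing | Known or expected pattern | Confirmed by stopping or reducing | Other causes |
|---|---|---|---|---|
| *Definitely*, limb 1 | not stated | previously known toxicity is enough | no | not stated |
| *Definitely*, limb 2 | required | required | required | no other reasonable explanation |
| *Probably* | required | required | required | other explanation unlikely |
| *Possibly* | required | required | not required | must be readily available |
| *Unrelated* | – | – | – | no relationship, with certainty |

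**Step 2. Apply the single dose.** Protocol Sections 8.7 and 17.4 fix exposure at one administration. The fourth column cannot be satisfied, which closes limb 2 of *Definitely* and all of *Probably*.

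**Step 3. Place four kinds of well-timed event**

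| Event | Level met |
|---|---|
| (a) Previously known toxicity | *Definitely*, limb 1 |
| (b) Known or expected pattern, other causes readily possible | *Possibly* |
| (c) Known or expected pattern, other causes unlikely | None, unless it counts as previously known toxicity. *Probably* fails on stopping or reducing; *Possibly* fails because no ready alternative exists |
| (d) New in nature, no known or expected pattern | None. Both limbs of *Definitely*, *Probably* and *Possibly* fail; *Unrelated* fails unless a relationship is excluded with certainty |

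*Probably* is met in 0 of the 4 cases. Case (d) has no related level at all.

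**Step 4. Compare with the SUSAR rule.** Protocol Section 12.1 treats an event as unexpected if its nature, severity or frequency is outside the prescribing information. Events unexpected in nature are case (d). Events unexpected only in severity or frequency can still follow a known pattern, so they can fall under (a) or (b).

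**Step 5. Expected numbers.** Protocol Section 2.1.2 lists reactions in 5, 4 and 3 of 747 patients. If no patient had two, that is 12/747 = 1.6%, or about 60 × 0.016 = 1 patient in this study. These are known reactions, so they fall under (a). The documents give no rate for (c) or (d).

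**The case against.** The case on the other side has real force.

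- **Serious events are still captured.** Protocol Section 12.4.1 sends every SAE to the sponsor's system within 24 hours with no causality filter, and the site reports all SAEs to the IRB/IEC. Section 17.6 repeats the duty to report immediately to the sponsor. Section 12.4.2 gives the sponsor the SUSAR reporting duty and does not name Table 5 as the test of suspicion. A reader might infer that the trial's expedited signal is disabled; these sections do not support that. The text of Section 12.5 (Medical Monitoring) was not available to this review, so a further causality check there cannot be excluded.
- **Not every unexpected reaction is affected.** A reader might infer that any unexpected reaction falls outside the scale. Step 4 shows otherwise: the gap is confined to reactions new in nature, plus case (c).
- **The pattern may be known *or expected*.** An anaphylactoid reaction soon after injection is a tempting example of the gap. Hypersensitivity is, however, already anticipated in exclusion criterion 5, so some would call it expected. The documents do not settle this, and the finding does not rest on it.
- **Table 5 is offered as guidelines.** Investigators may use judgement, and the certainty needed for *Unrelated*, together with the duty in Section 12.1 to record a cause when unrelated, pushes doubtful events away from that level. This stands, but no other criteria are supplied, so judgement would have to override the written definitions.
- **The SAP effect is modest.** TEAEs are also tabulated regardless of causality, attribution is mainly by time window, and counting blanks as related is conservative. The blank rule helps only if the field is left blank.

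**Conclusion.** The point holds. Applied as written, Table 5 makes one of its three related levels unreachable for every flotufolastat patient, leaves *Definitely* open only to previously known toxicity, and gives no level to a well-timed reaction new in nature. An event with an expected pattern and no likely alternative cause is also stranded unless it counts as known toxicity.

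The consequence is limited to classification: SUSAR status for reactions new in nature, the related-event tables, and attribution through SAP Table 3. SAE capture and the primary, secondary and tertiary endpoints are untouched. Few events are likely, so the effect concerns a rare signal rather than a rate.

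This rests on two assumptions: that the semicolon-separated conditions are joint, and that the known-toxicity limb of *Definitely* stands alone, which is the reading more favourable to the plan. A related omission adds to the problem: neither document says which Table 5 levels count as related.

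**What to change.** Revise Table 5 for a single administration.

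1. Delete the stopping or reducing element from *Definitely* and *Probably*.
2. In *Possibly*, remove both the pattern requirement and the competing-cause requirement. It then covers any event with a reasonable temporal sequence for which a causal role cannot be ruled out and which does not meet a higher level.
3. Keep *Unrelated* as the non-overlapping complement: events for which a causal role can be ruled out, including for lack of a plausible temporal link. Do not widen it to events with a more likely alternative cause. That would overlap with *Possibly* and could move events out of the related group.
4. State in the protocol and the SAP that *Definitely*, *Probably* and *Possibly* count as related, for SUSAR classification and for the tables.

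Re-running Step 3 on this wording, (a) is *Definitely*, (b) is *Possibly*, (c) is *Probably* or *Definitely*, and (d) is *Possibly*, so every case has a level.

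The cost is a change to the table wording, matching eCRF completion guidance and one sentence in the SAP. Any causality calls already recorded should be checked against the new wording before database lock. The downside is that a few more events may be classed as possibly related.

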12.4 Serious Adverse Events

A serious adverse event (SAE) is defined as any AE occurring at any dose that results in any of the following outcomes:

- Death;
- A life-threatening adverse experience;
- Inpatient hospitalization or prolongation of existing hospitalization;
- A persistent or significant disability/incapacity;
- A congenital anomaly/birth defect.

Other important medical events may also be considered an SAE when, based on appropriate medical judgment, they jeopardize the patient or require intervention to prevent one of the outcomes listed above.

12.4.1 Serious Adverse Event Reporting

Study sites will document all SAEs reported for piflufolastat (^{18}F) or flotufolastat (^{18}F) in the site's source documents and patient's eCRF. The collection period for SAEs will be the same as that for AEs, as defined in [Section 12.1](#).

All SAEs must be reported using the Electronic Data Capture (EDC) system within 24 hours of the Investigator becoming aware of the event.

The EDC system must be used to complete the SAE report form accurately and comprehensively.

In the event that the EDC system is unavailable, SAEs must be reported via email within the same 24-hour time-frame.

The email must include a completed SAE report form and be sent to the designated safety contact email address: [contact].

Once the EDC system is available, the SAE must be entered into the EDC system as soon as possible, and a note should be made indicating that the initial report was submitted via email.

Additional and further requested information (follow-up or corrections to the original event) will be detailed in EDC or on a new SAE Report Form and emailed to the same address if the EDC is unavailable.

As detailed in [Section 12.1](#), suspected adverse reactions for piflufolastat (^{18}F) should be reported to the Marketing Authorization Holder (Progenics Pharmaceuticals, Inc) or the FDA as detailed in the [PYLARIFY USPI](#).

For the US, in accordance with the standard operating procedures and policies of the local Institutional Review Board (IRB)/Independent Ethics Committee (IEC), the site investigator will report all SAEs to the IRB/IEC.

12.4.2 Suspected Unexpected Serious Adverse Reactions

Suspected unexpected serious adverse reactions (SUSARs) will be collected and reported for the IP, flutufolastat (^{18}F).

A serious adverse reaction is an adverse reaction, the nature and severity of which is not consistent with the reference safety information set out in the approved USPI for flutufolastat (^{18}F).

The sponsor will be responsible for reporting all SUSARs for flutufolastat (^{18}F) to the relevant authorities, IEC/IRB and other parties, as applicable.

Investigators will be informed of all SUSARs for flutufolastat (^{18}F) for all studies sponsored by BED, whether or not the event occurred in the current study.

As detailed in [Section 12.1](#), suspected adverse reactions for piflufolastat (^{18}F) should be reported to the Marketing Authorization Holder (Progenics Pharmaceuticals, Inc) or the FDA as detailed in the [PYLARIFY USPI](#).

13 DISCONTINUATION AND REPLACEMENT OF PATIENTS

13.1 Discontinuation/Withdrawal From the Study

Patients are free to withdraw from participation in the study at any time, for any reason, specified or unspecified, and without prejudice.

An investigator may discontinue or withdraw a patient for the following reasons:

- Significant non-compliance;
- If any clinical AE, laboratory abnormality, or other medical condition or situation occurs such that continued participation in the study would not be in the best interests of the patient;
- Protocol violation requiring discontinuation of study treatment;
- If the patient meets any exclusion criteria (either newly developed or not previously recognized) that precludes further study participation;
- Lost to follow-up;
- Sponsor request for early termination of study.

The reason for patient discontinuation or withdrawal from the study, if known, will be recorded in the patient's source documents and in the eCRF.

13.2 Additional Patients

In order to obtain a minimum of 52 evaluable patients (i.e., have evaluable PET scans for both piflufolastat (^{18}F) and flotufolastat (^{18}F) available for analysis), additional patients may be recruited if any patient does not receive **both** radiopharmaceuticals and have an evaluable PET scan for each.

13.3 Lost to Follow-up

A patient will be considered lost to follow-up if they fail to return for the second PET scan (flotufolastat (^{18}F)) within 10 calendar days of the first PET scan (piflufolastat (^{18}F)) and is unable to be contacted by the study site staff.

The following actions must be taken if a patient fails to return to the clinic for a required study visit:

- The site will attempt to contact the patient and reschedule the missed visit (no later than within 10 calendar days of the first PET scan) and counsel the patient on the importance of maintaining the assigned visit schedule and ascertain if the patient wishes to and/or should continue in the study;
- Before a patient is deemed lost to follow-up, the investigator or designee will make every effort to regain contact with the patient (where possible, three attempts to contact). These contact attempts should be documented in the patient's medical record or study file;
- Should the patient continue to be unreachable, they will be considered to have withdrawn from the study with a primary reason of lost to follow-up.

14 **PROTOCOL VIOLATIONS**

A protocol violation occurs when the patient, investigator, or sponsor fails to adhere to significant protocol requirements affecting the inclusion, exclusion, patient safety, and primary endpoint criteria. Protocol violations for this study include, but are not limited to, the following:

- Failure to meet inclusion/exclusion criteria (see [Sections 6.2](#) and [6.3](#));
- Use of a prohibited concomitant medication (see [Section 7.2](#));
- Radiopharmaceutical administration but no subsequent PET scan;
- Use of a non-approved PET/CT scanner.

Significant non-compliance with Good Clinical Practice (GCP) guidelines will also result in a protocol violation. The sponsor will determine if a protocol violation will result in the withdrawal of a patient.

When a protocol violation occurs, it will be discussed with the investigator and a protocol violation form detailing the violation will be generated. This form will be signed by a sponsor representative and the investigator. A copy of the form will be filed in the investigator site's file and in the sponsor's files.

15 STATISTICAL METHODS AND CONSIDERATIONS

Prior to the analysis of the final study data, a detailed Statistical Analysis Plan (SAP) will be written describing all analyses that will be performed. The SAP will contain any modifications to the analysis plan described below.

15.1 Estimation of Sample Size

Approximately 60 patients will be screened for inclusion into the study to obtain a minimum of 52 evaluable patients (i.e., have evaluable PET scans for both piflufolastat (^{18}F) and flotufolastat (^{18}F) available for analysis).

A sample size of 52 evaluable patients achieves 80% power to detect a mean of paired differences of 10 in SUV_{mean} , with an estimated standard deviation of paired differences of 25 and with a significance level of 0.05 using a two-sided paired Wilcoxon signed-rank test assuming that the actual distribution of paired differences is uniform.

The difference in SUV_{mean} of 10 is based on the difference in the median bladder SUV_{mean} values of 25.4 observed for another renally cleared PSMA PET ligand, ^{68}Ga -PSMA-11 (Kuten et al, 2020) and 12.5 observed for flotufolastat (^{18}F) (Kuo et al, 2024; see Figure 3, Section 1.3).

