Rationale for Number of Patients	
Approximately 60 patients will be screened for inclusion into the study to obtain a minimum of 52 evaluable patients (i.e., have evaluable PET scans for both piflufolastat (^{18}F) and flutufolastat (^{18}F) available for analysis).
 
A sample size of 52 evaluable patients achieves 80% power to detect a mean of paired differences of 10 in SUV_{mean}, with an estimated standard deviation of paired differences of 25 and with a significance level of 0.05, using a two-sided paired Wilcoxon signed-rank test, assuming that the actual distribution of paired differences is uniform.
	

STUDY SCHEMA

Figure 1: Overall Study Design

Abbreviations: ¹⁸F=fluorine-18; PET=positron emission tomography.

^a Visit 1 (screening) and Visit 2 (Scan 1) may be combined if the investigator decides to screen a patient and perform the piflufolastat (¹⁸F) PET scan on the same day. In such cases, all assessments listed for Visit 1 (screening) should be performed **prior to** the piflufolastat (¹⁸F) injection and PET scan. If Visit 1 (screening) and Visit 2 (Scan 1) are combined, the investigator should ensure ample time is made available for the patient to think about the study and ask questions before agreeing to participate (see [Section 17.3](#) for details of informed consent requirements).

^b Approximately 60 patients will be screened for inclusion into the study to obtain a minimum of 52 evaluable patients (i.e., have evaluable PET scans for both piflufolastat (¹⁸F) and flotufolastat (¹⁸F) available for analysis).

- ^c The flutufolastat (¹⁸F) PET scan should occur at least 24 hours later than, but within 10 calendar days of the piflufolastat (¹⁸F) scan.

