## 11. Sample Size Determination

Approximately 60 patients will be screened for inclusion into the study to obtain a minimum of 52 evaluable patients (i.e. have evaluable PET scans for both piflufolastat (18F) and flutufolastat (18F) available for analysis).

A sample size of 52 evaluable patients achieves 80% power to detect a mean of paired differences of 10 in  $SUV_{mean}$ , with an estimated STD of paired differences of 25 and with a significance level of 0.05 using a two-sided paired Wilcoxon signed-rank test assuming that the actual distribution of paired differences is uniform.

The difference in  $SUV_{mean}$  of 10 is based on the difference in the median bladder  $SUV_{mean}$  values of 25.4 observed for another renally cleared PSMA PET ligand, 68Ga-PSMA-11 (Kuten, et al., 2020) and 12.5 observed for flutufolastat (18F) (Kuo, et al., 2024).

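### With 52 patients, the signed-rank test on uniform differences has about 74.5% power, not the stated 80%

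*Protocol*

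**What the plan says.** Protocol 15.1 gives every input to the power calculation. Its claim is this: "A sample size of 52 evaluable patients achieves 80% power to detect a mean of paired differences of 10". The quantity is bladder SUVmean, the SD of the differences is put at 25, and the primary test is the signed-rank test, two-sided at 0.05. The distribution is also fixed. The protocol synopsis makes the calculation "assuming that the actual distribution of paired differences is uniform", and SAP section 11 names the same test and shape: "using a two-sided paired Wilcoxon signed-rank test assuming that the actual distribution of paired differences is uniform". None of the three places names a formula, an approximation or software.

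On recruitment, protocol 15.1 says "Approximately 60 patients will be screened for inclusion into the study to obtain a minimum of 52 evaluable patients".

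Protocol 15.4 makes the signed-rank test the primary test without condition. SAP 4.1.2 keeps it when the differences look non-normal on histograms and Q-Q plots, and uses a paired t-test when they look normal.

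**The concern.** At a standardised effect of 10/25 = 0.4, 52 is the usual answer for a paired t-test. The signed-rank test would have the same sample size only if it were as efficient as the t-test at that effect. For uniform data the asymptotic relative efficiency is 1.0, but that is a limit for shifts close to zero. A shift of 0.4 SD on a bounded, flat distribution is not close to zero, so the actual power needed checking.

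This is the only hypothesis test in the study with a stated power. If the figure is too high, the three places credit the design with a power it does not have under its own assumptions, and anyone weighing a non-significant result would be working from the wrong type II error.

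**Working it through.** **Inputs** (protocol 15.1, repeated in the synopsis and SAP 11): n = 52 pairs, mean difference 10, SD 25, two-sided alpha 0.05, signed-rank test, uniform differences.

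**1. Reproducing the stated figure.** Paired t-test power from the noncentral t, with noncentrality 0.4 × √n:

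- n = 51: 79.99%
- n = 52: 80.8% (noncentrality 0.4 × √52 = 2.88)

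So 52 is the first n to reach 80%. Multiplying n by a relative efficiency of 1 leaves it at 52. The stated figure is therefore consistent with a t-test calculation carried over through the uniform efficiency. The documents do not say that this was the route.

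**2. The uniform distribution implied.** Half-width L = 25 × √3 = 43.3, so the differences run from 10 − 43.3 = −33.3 to 10 + 43.3 = 53.3, a width of 86.6.

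**3. Why the shortcut fails at this shift.** The signed-rank statistic depends mainly on p2, the probability that the sum of two independent differences is positive.

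- For a uniform shifted by δ: p2 = 1 − ½(1 − δ/L)², so p2 − ½ = δ/L − δ²/(2L²).
- Linear term: 10/43.3 = 0.2309. Using this alone, √(3n) × 0.2309 = √156 × 0.2309 = 2.88, the same as the t-test. This is the relative efficiency of 1.
- Quadratic term: 100/(2 × 1875) = 0.0267. Subtracting it leaves p2 − ½ = 0.2043, so p2 = 0.7043.
- With the quadratic term: √156 × 0.2043 = 2.55. Noether's approximation then gives Φ(2.55 − 1.96) = 72.3% power and a sample size of 63.

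From the exact mean of the statistic:

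- p1 = P(difference > 0) = 53.3/86.6 = 0.6155.
- E(W) = 52 × 0.6155 + (52 × 51/2) × 0.7043 = 965.9.
- Null mean 52 × 53/4 = 689; null SD √(52 × 53 × 105/24) = 109.8.
- Standardised shift (965.9 − 689)/109.8 = 2.52, against 2.88 for the t-test.

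**4. Direct simulation of the named test.** 400,000 trials at n = 52, differences uniform on −33.3 to 53.3, rejection by the exact null distribution (true size 0.049):

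- Signed-rank power: **74.5%** (Monte Carlo standard error √(0.745 × 0.255/400,000) = 0.07 points). The normal approximation, with or without continuity correction, gives the same figure.
- Paired t-test on the same simulated data: 80.8%.
- One-sided 0.05 signed-rank test: 83.8%, so a one-sided calculation does not explain the 80% either.

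**5. Sample size for 80%** (200,000 trials each, same assumptions): 79.2% at n = 58, 79.9% at 59 and 80.6% at 60.

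**6. Other assumptions, signed-rank test, n = 52, SD 25:**

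| Differences | Mean difference | Power |
|---|---|---|
| Uniform | 10 | 74.5% |
| Normal | 10 | 78.9% |
| Logistic | 10 | 83.5% |
| Double exponential | 10 | 90.0% |
| Uniform | 12.9 (= 25.4 − 12.5) | about 92% |

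**The case against.** The 80% is not a slip in arithmetic. It reproduces as a standard large-sample shortcut, and the uniform shape is only a planning device; nothing in the documents says that SUVmean differences are expected to be uniform. With normal differences the shortfall is about 1 point, and with the heavier-tailed symmetric shapes tried there is none. If the differences look normal, SAP 4.1.2 switches to the t-test, which has about 80.8%. The difference of 10 is below the 12.9 gap between the cited medians, and the SD of 25 has no stated source, so uncertainty in those inputs may outweigh a 5.5-point approximation error. The 52 is also a minimum, and planned power does not enter the p-value or the type I error.

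Most of this stands, and it limits how serious the point is. It does not make the sentence true. The documents name the test and the distribution and mention no approximation. The t-test branch does not help under the plan's own assumption, because a uniform distribution is not normal and the SAP rule then calls for the signed-rank test. The minimum gives little cover either. Protocol 13.2 allows additional recruitment in order to reach 52, not 59 or 60, and with about 60 screened, 59 to 60 evaluable would leave almost no room for loss.

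**Conclusion.** The power statement is wrong as written. Under the stated assumptions 52 evaluable patients give 74.5%, which is 5.5 points below the stated 80%, and the type II error is 25.5% rather than 20%. The calculation needs no assumption beyond those printed in the plan. That the t-test shortcut is the cause is an inference, although it accounts for the 52 exactly.

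The size of the gap depends on the uniform shape. It shrinks to about 1 point for normal differences and vanishes for the logistic and double exponential shapes. Skewed shapes were not calculated. At a true difference of 12.9 the design has about 92% power even with uniform differences. The design is therefore serviceable, and the validity of the primary test is unaffected. The statement should be corrected, but the correction does not call for a redesign.

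**What to change.** Replace the power statement in protocol 15.1, the protocol synopsis and SAP section 11 with wording to this effect:

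> With 52 evaluable patients, a two-sided paired Wilcoxon signed-rank test at the 0.05 level has about 75% power, by simulation, if the paired differences are uniform with mean 10 and SD 25. Power is about 79% if the differences are normal with the same mean and SD, and about 92% if they are uniform with mean 12.9.

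It would help to add that the paired t-test, which SAP 4.1.2 uses if the differences look normal, has about 81% power at mean 10 and SD 25.

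The cost is wording only, and the headline figure becomes slightly less favourable. No patients, visits or analyses change. Changing the protocol text means following the amendment process in protocol 17.2. If the sponsor does not want to amend for this alone, SAP section 11 can carry the corrected figure, since protocol section 15 lets the SAP modify the statistical plan. Should the sponsor wish to keep 80% under the uniform assumption, the evaluable target would have to rise to about 60, and the number screened would have to rise with it.
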